6.5.2. Additional considerations

Standard data derivation procedures for safety are available in Section 11 (see Section 11.2.5).

Note that the study will be converted in cDISC. Accordingly Day 0-Day N will be replaced by Day 1-Day N+1 for the statistical analysis.

A summary of subjects with all combined solicited (regardless of their duration) and unsolicited AEs will be provided. Solicited AEs will be coded by MedDRA as per the following codes:

Solicited symptom	Lower level term code	Corresponding Lower level term decode
Pain at injection site	10022086	Injection site pain
Redness at injection site	10022098	Redness at injection site
Swelling at injection site	10053425	Swelling at injection site
Drowsiness	10013649	Drowsiness
Fever	10016558	Fever
Irritability/Fussiness	10057224	Irritability post vaccinal
Loss of appetite	10003028	Appetite lost
Measles-like rash	10027022	Measles-like rash

Cases of measles and rubella will be listed.

6.5.2.1. Concomitant Medication and Concomitant Vaccination

Medications will be coded using the GSKDRUG dictionary.

The frequencies and percentages of subjects reporting antipyretic medications will be tabulated by vaccine group for each study dose and across doses. All concomitant medication will be provided in individual listings.

Antipyretics will be further considered prophylactic when administered in the absence of ANY symptom and in anticipation of a reaction to the vaccination.

Concomitant vaccinations administered in the period starting seven days before the first dose of study vaccine and ending at Visit 5 (Month 4) will be listed.

7. ANALYSIS INTERPRETATION

Except for analyses on objectives with a pre-defined success criterion (see Section 3), comparative analyses will be descriptive with the aim to characterize the difference in immunogenicity and safety between groups.

8. CONDUCT OF ANALYSES

8.1. Sequence of analyses

Description	Analysis ID	Disclosure Purpose (CTRS=public posting, SR=study report, internal)	Dry run review needed (Y/N)	Study Headline Summary (SHS) requiring expedited communication to upper management (Yes/No)	Reference for TFL
Final analysis	E1_01	SR, CTRS	Y	Yes	TFL_TOC_MAL-073
Primary Epoch Analysis	E1_02	SR, CTRS	Y	Yes	TFL_TOC_MAL-073

The primary analysis will be performed on data collected up to and including 42 days post-measles/rubella/YF vaccination and will include all immunogenicity data (primary secondary and tertiary endpoints) and safety data (secondary endpoints) up to Month 4.5 (Visit 6). A clinical study report will be written after this analysis.

An analysis with remaining safety data will be performed when all data up to and including the Month 33 for Coad and RTS,S groups (Visit 14) and Month 36 for the Control group (Visit 15) will be available. Additional safety information will be added to the clinical study report prepared after Visit 6.

8.2. Statistical considerations for interim analyses

No interim analyses are planned.

9. CHANGES FROM PLANNED ANALYSES

The seropositivity threshold for anti-CS has been updated from 0.5 EU/ml to 1.9 EU/ml.

10. LIST OF FINAL REPORT TABLES, LISTINGS AND FIGURES

The TFL TOC provides the list of tables/listings and figures needed for the study report. It also identifies the tables eligible for each analysis and their role (synopsis, in-text, post-text, SHS, CTRS,...). Note that all TFL aimed to be included as post-text are noted as post-text even if these are tabulation of individual data such as listing of SAE. The post-text material contains all source material for the study report and accordingly a post-text table may be redundant with an in-text table.

The mock tables referred under column named 'layout' can be found in Section 13 of this SAP.

The following group names will be used in the TFLs, to be in line with the T-domains:

Group order in tables	Group label in tables	Group definition for footnote	Pooled Groups label in tables	Pooled definition for footnote
1	Coad	Group receiving co-administration regimen of RTS,S/AS01 _E , YF vaccine and a combined measles and rubella vaccine	NA	NA
2	RTS,S	Group receiving regimen of RTS,S/AS01 _E vaccine	NA	NA
3	Control	Group receiving regimen of YF vaccine and a combined measles and rubella vaccine	NA	NA

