- Control: active control (Group receiving the EPI interventions alone [Vitamin A at 6 months and YF vaccine and a combined measles and rubella vaccine at 9 months of age]). Children from this group will receive a 3-dose course (0, 1, 2-month) and a booster dose (17.5 months post Dose 3) of RTS,S/AS01_E from Visit 6 onwards (10.5 months of age) so they can benefit from the same protection as the children from the Coad and the RTS,S groups.
- Vaccination schedules:
 - For the **Coad group**, children will receive Vitamin A and RTS,S/AS01_E vaccine on Day 0 (Visit 2 [6 months of age]), RTS,S/AS01_E alone at Visit 3 (7.5 months of age), co-administration of RTS,S/AS01_E, YF vaccine and a combined measles and rubella vaccine at Visit 4 (9 months of age), and a booster dose of RTS,S/AS01_E at Visit 10 (27 months of age).
 - For the **RTS,S group**, children will receive Vitamin A and RTS,S/AS01_E vaccine on Day 0 (Visit 2 [6 months of age]), RTS,S/AS01_E alone at Visit 3 and 4 (7.5 and 9 months of age), YF vaccine and a combined measles and rubella vaccine at Visit 6 (10.5 months of age), and a booster dose of RTS,S/AS01_E at Visit 10 (27 months of age).
 - For the **Control group**, children will receive Vitamin A on Day 0 (Visit 2 [6 months of age]) and YF vaccine and a combined measles and rubella vaccine at Visit 4 (9 months of age). These children will also receive RTS,S/AS01_E vaccine at Visit 6, 7 and 8 (10.5, 11.5 and 12.5 months of age) and a booster dose of RTS,S/AS01_E vaccine at Visit 12 (30 months of age).
- Treatment allocation: randomized in a 1:1:1 ratio to each study group.
- Blinding: open

Table 3 Blinding of study epoch

Study Epoch	Blinding
Epoch 001	open

- Sampling schedule:
 - For the **Coad group**, blood samples will be taken on Day 0, on the day of co-administration of RTS,S/AS01_E with the YF vaccine and the combined measles

and rubella vaccine (Month 3) and at one month post co-administration (Month 4).

- For the **RTS,S group**, blood samples will be taken on Day 0 and at one month post Dose 3 of RTS,S/AS01_E (Month 4).
- For the **Control group**, blood samples will be taken on Day 0, on the day of administration of the YF vaccine and the combined measles and rubella vaccine (Month 3) and at one month post-vaccination with the YF vaccine and the combined measles and rubella vaccine (Month 4).
- Type of study: self-contained.
- Data collection: Electronic Case Report Form (eCRF).
- Safety monitoring:

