8.1.5.3. Meningitis (Amended: 09 August 2016)

For the further evaluation of the safety signal of meningitis all the cases occurring during the study will be reported as SAE and medical documentation of the events will be reported in *specific eCRF screens*. Cerebrospinal fluid will be frozen for future testing for infectious agents if applicable (this procedure is fully described in the SPM).

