2. STUDY DESIGN

Figure 1 Study design

- Experimental design: Phase IIIB, open, randomized, controlled, multi-centric study with three parallel groups.
- Duration of the study: Approximately 33 months per participant in the Coad or the RTS,S group and 36 months in the Control group.
 - Epoch 001: Primary starting at Visit 1 (Screening) and ending at Visit 15 (Month 36).
- Study groups: 3 study groups are defined for the study (Coad group, RTS,S group and Control group). A description of the vaccination, blood sample and visit schedule is provided for each of the study groups in [Figure 1](#).

Table 1 Study groups and epochs foreseen in the study

Study groups	Number of subjects	Age (Min)	Epoch 001
Coad group	233	6 months*	X
RTS,S group	233	6 months*	X
Control group	233	6 months*	X

* For clarity this corresponds from the day the child becomes 6 months of age until the day before the child achieves 7 months of age.

Table 2 Study groups and treatment foreseen in the study

Treatment name	Vaccine/Product name	Study groups		
		Coad group	RTS,S group	Control group
RTS,S/AS01 _E	RTS,S	X	X	X
	AS01E	X	X	X
Yellow fever	WHO prequalified Yellow Fever	X	X	X
Measles and Rubella	MR-VAC	X	X	X
Vitamin A	Vitamin A	X	X	X

MR-VAC: Live attenuated measles virus and rubella virus vaccine (Serum Institute of India)

- Treatment allocation: randomized in a 1:1:1 ratio to each study group.
- Blinding: open

Table 3 Blinding of study epoch

Study Epoch	Blinding
Epoch 001	open

- Type of study: self-contained.
- Data collection: Electronic Case Report Form (eCRF).
- Safety monitoring: description of safety monitoring is available in [Table 5](#)
- Immunogenicity monitoring:

Table 4 Immunological read-outs

Blood sampling timepoint		study group	No. subjects	Component	Components priority rank
Type of contact and timepoint	Sampling timepoint				
Visit 2	Day 0	Coad group and RTS,S group	466	anti-CS	1
		Coad group and RTS,S group	466	anti-HBs	2
		Coad group and Control group	466	anti-catalase	3
Visit 4	Month 3	Coad group and Control group	466	anti-Me	1
		Coad group and Control group	466	anti-Ru	2
Visit 5	Month 4	Coad group and RTS,S group	466	anti-CS	1
		Coad group and RTS,S group	466	anti-HBs	5
		Coad group and Control group	466	anti-catalase	6
		Coad group and Control group	466	anti-Me	2
		Coad group and Control group	466	anti-Ru	3
		Coad group and Control group	466	anti-YF	4

Table 5 Reporting periods for adverse events and serious adverse events

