6.5. Analysis of safety

6.5.1. Analysis of safety planned in the protocol

The primary analysis will be based on the ES.

The percentage of subjects with at least one local AE (solicited and unsolicited), with at least one general AE (solicited and unsolicited) and with any AE during the solicited follow-up period [7 days post Dose 1, post Dose 2 and 14 days post Dose 3] will be tabulated with exact 95% CI after each vaccine dose and overall. The percentage of doses followed by at least one local AE (solicited and unsolicited), by at least one general AE (solicited and unsolicited) and by any AE will be tabulated for the overall vaccination course, with exact 95% CI. Similar tables will be generated for Grade 3 AEs and AEs considered as causally related to vaccination.

The percentage of subjects reporting each individual solicited local and general AE during the solicited follow-up period will be tabulated with exact 95% CI. The percentage of doses followed by each individual solicited local and general AE will be tabulated for each dose and for the overall vaccination course, with exact 95% CI. Similar tables will be generated for Grade 3 AEs, causal events and for fever, temperature in 0.5°C increments.

The proportion of subjects reporting an AE (unsolicited) until 30 days (Days 0-29) post each dose of RTS,S/AS01_E, classified by the Medical Dictionary for Regulatory Activities (MedDRA) preferred term level will be tabulated with exact 95% CI. The proportion of subjects reporting an AE (unsolicited) until 42 days (Days 0-41) after the administration of the YF vaccine and the combined measles and rubella vaccine (restricted to the Coad group and Control group), classified by the MedDRA preferred term level will be tabulated with exact 95% CI. Similar tables will be generated for Grade 3 AEs and AEs considered as causally related to vaccination.

The proportion of subjects reporting an SAE (all, fatal, related) occurring within 30 days (day of vaccination and 29 subsequent days) after each visit where a study product is potentially administered, classified by the MedDRA preferred term level will be tabulated with exact 95% CI.

The proportion of subjects reporting an SAE (all, fatal, related) from Day 0 to Month 4.5 and over the whole study duration (Day 0 to Month 33 for Coad and RTS,S groups and Month 36 for the Control group), classified by the MedDRA preferred term level will be tabulated with exact 95% CI.

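### Whole-study safety tables keep one Control column, footnoted as yellow fever and measles-rubella recipients, although 87.5% of Control follow-up comes after the first RTS,S dose

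*SAP*

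**What the plan says.** Protocol Section 3 gives Control the yellow fever (YF) and measles-rubella (MR) vaccines at Visit 4 and then RTS,S: "These children will also receive RTS,S/AS01_E vaccine at Visit 6, 7 and 8 (10.5, 11.5 and 12.5 months of age"), followed by "a booster dose of RTS,S/AS01_E vaccine at Visit 12 (30 months of age"). The RTS,S group receives YF and MR at Visit 6. SAP Table 2 accordingly marks RTS,S, YF and MR for all three groups.

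SAP 6.5.1 tabulates the proportion of subjects with SAEs, and with adverse events of specific interest (pIMDs, meningitis, seizures), for two periods. One is Day 0 to Month 4.5. The other is "over the whole study duration (Day 0 to Month 33 for Coad and RTS,S groups and Month 36 for the Control group").

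SAP Section 10 fixes the group labels for the tables. Control is footnoted as "Group receiving regimen of YF vaccine and a combined measles and rubella vaccine", and the RTS,S group as receiving an RTS,S regimen. No pooled group is defined. Template 46, the mock table for SAEs over the study period, has one column per group. SAP 5.1.2 analyses the Exposed Set by treatment actually administered, but no rule divides a child's follow-up at the first RTS,S dose.

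**The concern.** In any table that runs past Visit 6, the Control footnote omits RTS,S and the RTS,S-group footnote omits YF and MR. A reader of the whole-study SAE table, especially where results are posted without the protocol, could take Control to be unexposed to RTS,S and read similar columns as evidence of no RTS,S effect.

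This matters most for outcomes that can arise late. Protocol 1.3.1 lists meningitis and pIMDs as important potential risks of RTS,S, and Protocol 8.1.5.3 states the purpose of collecting meningitis: "For the further evaluation of the safety signal of meningitis all the cases occurring during the study will be reported as SAE". A Control case many months after an RTS,S dose would appear in a column described as YF plus MR.

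**Working it through.** **Inputs from the documents.** Control starts RTS,S at 10.5 months of age and is boosted at 30 months; the other groups are boosted at 27 months. Entry is at 6 months of age, and follow-up runs 12 months past the last dose. Enrolment is 233 per group.

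**The plan's own figures, reproduced.**
- Crossover: 10.5 − 6 = 4.5, matching "safety data (secondary endpoints) up to Month 4.5 (Visit 6").
- Follow-up: 27 − 6 + 12 = 33 months and 30 − 6 + 12 = 36 months, matching "Approximately 33 months per participant in the Coad or the RTS,S group and 36 months in the Control group".
- Group size: 205 / (1 − 0.12) = 232.95, so 233.

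The documents give no power or precision for any safety contrast.

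**Exposed share of Control follow-up.** (36 − 4.5)/36 = 31.5/36 = 87.5%. Allowing about one month after each of four doses for the 30-day windows, 31.5 − 4 = 27.5 months (27.5/36 = 76%) lie after first RTS,S but outside every window.

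**Model A, persistent effect (assumption).** A constant background rate is multiplied by k from the first RTS,S dose onward. In units of the background rate per month:
- Coad (or RTS,S group): 33k
- Control: 4.5 + 31.5k
- Ratio of rare-event proportions: 33k/(4.5 + 31.5k)
- Ratio per child-month: 36k/(4.5 + 31.5k)

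| k | Proportions | Per child-month |
|---|---|---|
| 1 | 33/36 = 0.92 | 1.00 |
| 2 | 66/67.5 = 0.98 | 72/67.5 = 1.07 |
| 3 | 99/99 = 1.00 | 108/99 = 1.09 |
| 5 | 165/162 = 1.02 | 180/162 = 1.11 |
| 10 | 330/319.5 = 1.03 | 360/319.5 = 1.13 |

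The first row separates two effects. The 0.92 comes only from 33 versus 36 months of follow-up. The per-child-month column removes that imbalance, and the contrast is still close to 1 because exposure is nearly the same in the two columns.

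**Model B, effect limited to one month after each of four doses (assumption).** The proportion ratio is [33 + 4(k − 1)]/[36 + 4(k − 1)]: 37/40 = 0.93 at k = 2 and 49/52 = 0.94 at k = 5. Per child-month these become (37/33)/(40/36) = 1.01 and (49/33)/(52/36) = 1.03.

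**The uncontaminated period, Day 0 to Month 4.5.** Under Model A the expected ratio is k itself. Under Model B, with three doses in the period, it is [4.5 + 3(k − 1)]/4.5: 1.67, 2.33 and 3.67 for k = 2, 3 and 5.

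**Power, as a check on what a clean contrast can deliver.** Proportions are 1 − exp(−cumulative hazard), with 233 per group, one RTS,S-containing arm versus Control, and assumed background rates.
- Whole study, k = 2 to 5, 0.5 to 200 events per 1000 child-years: 2.5% to 3.8%, about the one-sided error rate.
- To Month 4.5 under Model A, k = 2, 3, 5: 6%, 10% and 19% at 5 per 1000 child-years; 22%, 55% and 93% at 50 per 1000.

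**The case against.** The strongest reply is that the plan does not rely on the diluted contrast.

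- **Safety objective.** It compares co-administration with RTS,S given alone, that is Coad versus the RTS,S group. Both have the same RTS,S schedule and 33 months of follow-up, so the Control crossover does not touch it. Comparative safety analyses are descriptive. This stands.
- **Clean period.** SAP 6.5.1 already tabulates SAEs and events of specific interest to Month 4.5, before Control starts RTS,S. This stands, and a pre-crossover Control column largely repeats that table.
- **Post-dose tables.** Control has its own endpoints for unsolicited events and seizures within 30 days of Visits 6, 7, 8 and 12, and SAEs are tabulated for 30 days after each product visit. Meningitis and pIMDs are reported as SAEs, so they enter those tables. A reader might infer that Control's RTS,S experience is lost from the safety description; the documents do not support that. The gap is events outside those windows.
- **Missing mocks.** Annex 3 has no whole-study table for meningitis or pIMDs, and the list of tables is not in the documents. The single column is documented for SAEs and inferred for the other two. SAP Section 13 allows minor changes to displays without amendment, but a split by exposure is more than that.
- **Other places state the crossover.** The protocol's design sections do so clearly, and SAP Table 2 marks RTS,S for every group. That lowers the risk of misreading but does not make the footnotes correct.

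Two further inferences should be resisted. The 0.98 at k = 2 is not dilution alone, since unequal follow-up gives 0.92 with no effect. Nor would splitting Control follow-up create a randomised comparison after Visit 6, or much power for rare events.

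**Conclusion.** The point holds as one of labelling and attribution in tables that run past Visit 6, and should be corrected. The Section 10 footnotes are incomplete there for Control and for the RTS,S group. Treating exposed by treatment received does not help, because crossover is part of the assigned Control regimen and the rule does not divide a child's time.

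Over the whole study, a persistent two- to fivefold effect would appear as 1.07 to 1.11 per child-month, or 0.98 to 1.02 as proportions. A short post-dose effect would be even less visible. These figures assume full follow-up on schedule, a constant background rate and the stated values of k, none of which the documents supply for safety outcomes. The 87.5% share depends only on the visit schedule.

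A reader might infer that the trial's safety conclusion is biased. The documents do not support that: the stated objective, the Month 4.5 tables and the 30-day post-dose tables are unaffected. What is misattributed is mainly Control SAEs, meningitis and pIMDs arising more than 30 days after an RTS,S dose.

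**What to change.** 1. In SAP Section 10, for tables running past Visit 6, give the full regimens in the footnotes: RTS,S from Visit 6 in Control, and YF plus MR at Visit 6 in the RTS,S group.
2. In SAP 6.5.1 and Template 46, and in the whole-study tables for events of specific interest, show Control events separately before and after each child's own first RTS,S dose, with child-time denominators. SAP 11.2.2 already assigns an event on the day of a dose to that dose, which settles events on the crossover day.
3. State that Day 0 to Month 4.5 is the only randomised RTS,S versus no-RTS,S contrast.
4. Optionally, add a table aligned on first RTS,S dose. Label it descriptive and non-randomised: Control starts at 10.5 rather than 6 months of age, on a 0, 1, 2-month rather than a 0, 1.5, 3-month schedule, and has 31.5 rather than 33 months of follow-up after first dose.

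The cost is SAP wording and slightly longer tables. Vaccination and onset dates are already used in the SAP derivations, so no new data are needed.

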11. ANNEX 1 STANDARD DATA DERIVATION RULE AND STATISTICAL METHODS

11.1. Statistical Method References

The exact two-sided 95% CIs for a proportion within a group will be the Clopper-Pearson exact CI [Clopper CJ, Pearson ES. The use of confidence or fiducial limits illustrated in the case of binomial. *Biometrika*. 1934;26:404-413].

The standardised asymptotic two-sided 95% CI for the group difference in proportions is based on the method described in the following paper: Robert G. Newcombe, interval estimation for the difference between independent proportions: comparison of eleven methods, *Statist Med*. 1998; 17, 873-890]. The standardised asymptotic method used is the method six.

11.2. Standard data derivation

11.2.1. Date derivation

- SAS date derived from a character date: In case day is missing, 15 is used. In case day & month are missing, 30June is used.
- The onset day for a safety event is the number of days between the last study vaccination and the onset/start date of the event (onset date – last study vaccination+1). This is 1 for an event starting on the same day as a vaccination.
- Duration: Duration of an event is expressed in days. It is the number of days between the start & the stop dates + 1. Therefore duration is 1 day for an event starting & ending on the same day.

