For the **Coad group** and the **RTS,S group**, there will be:

- A 7-day follow-up period (day of vaccination and 6 subsequent days) following vaccines administered at 6 and 7.5 months of age (Visits 2 and 3) for recording of solicited local and general adverse events (AEs). On the day of vaccination the evaluation will be carried-out by the study physician at the study center. On Days 1, 2, 3, 4, 5 and 6 after vaccination, trained study personnel will visit the children to record solicited AEs on diary cards.
- A 14-day follow-up period (day of vaccination and 13 subsequent days) following vaccines administered at 9 months of age (Visit 4) for recording of solicited local and general AEs. On the day of vaccination the evaluation will be carried-out by the study physician at the study center. On Days 1 to 13 after vaccination, trained study personnel will visit the children to record solicited AEs on diary cards.
- Unsolicited AEs will be collected from the day of first vaccine administration (Visit 2) until 42 days after Visit 4. On the days of vaccinations (Visits 2, 3 and 4) the evaluation will be carried-out by the study physician at the study center. Unsolicited AEs will be captured through passive surveillance at inpatient and outpatient facilities and during study visits. In addition on Days 1 to 6 after vaccinations at Visits 2 and 3 and on Days 1 to 13 after Visit 4, trained study personnel will visit the children to record any unsolicited AEs on diary cards.
- A 30-day follow-up period (day of vaccination and 29 subsequent days) after booster dose of RTS,S/AS01_E vaccines administered at 27 months of age (Visit 10) for reporting unsolicited AEs. Unsolicited AEs will be captured through passive surveillance at inpatient and outpatient facilities and during study visits.

For the **Control group**, there will be:

A 7-day follow-up period (day of administration and 6 subsequent days) following Vitamin A administered at 6 months of age (Visit 2) and a 7-day follow-up period following Visit 3 (7.5 months of age) for recording of solicited general AEs. On the day of Visits 2 and 3 the evaluation will be carried-out by the study physician at the study center. On Days 1, 2, 3, 4, 5 and 6 after Visits 2

and 3, trained study personnel will visit the children to record solicited general AEs on diary cards.

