11.2.2. Dose number

- The study dose number is defined in reference to the number of study visits at which vaccination occurred. More specifically dose 1 refers to all vaccines administered at the first vaccination visit while dose 2 corresponds to all vaccinations administered at the second vaccination visit even if this is the first time a product is administered to the subject.
- Relative dose: the relative dose for an event (AE, medication, vaccination) is the most recent study dose given before an event. In case the event takes place on the day a study dose is given, the related dose will be that of the study dose, even if the event actually took place before vaccination. For instance, if an adverse event begins on the day of the study vaccination but prior to administration of the vaccine, it will be assigned to this dose. In case a study dose is not administered and an event occurs after the subsequent study dose (eg 3rd study dose), the relative dose of the event will be study dose associated to the subsequent study dose (eg dose 3).
 - The number of doses for a product is the number of time the product was administered to a subject.
 - The incidence per dose is the number of vaccination visits at which an event was reported among all vaccination visits.

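### SAP 11.2.1 fills partial onset dates with the 15th or 30 June without looking at the dose date, so partly dated AEs and SAEs can be moved out of, or into, a post-dose window

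*SAP*

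**What the plan says.** SAP 11.2.1 (Date derivation) covers any SAS date built from a character date: "In case day is missing, 15 is used. In case day & month are missing, 30June is used". No type of date is exempt.

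The next bullet uses such a date: "The onset day for a safety event is the number of days between the last study vaccination and the onset/start date of the event", plus one, with the check value "This is 1 for an event starting on the same day as a vaccination". SAP 11.2.2 then assigns the event to a dose: "the relative dose for an event (AE, medication, vaccination) is the most recent study dose given before an event". An event on the day of a dose goes to that dose, even if it began before the injection.

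SAP 6.5.1 counts events in windows that depend on these derivations:
- unsolicited AEs: "The proportion of subjects reporting an AE (unsolicited) until 30 days (Days 0-29) post each dose of RTS,S/AS01_E", and Days 0-41 after the yellow fever and measles-rubella vaccines;
- SAEs: 30 days after each visit at which a product may be given;
- generalized convulsive seizures: 7 days after Visits 2 and 3, and 14 days after Visit 4.

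Protocol Section 3 plans daily home visits on Days 1-6 after Visits 2 and 3 and on Days 1-13 after Visit 4. Otherwise, "Unsolicited AEs will be captured through passive surveillance at inpatient and outpatient facilities and during study visits".

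Neither document bounds an imputed onset at the dose date or says what to do when it precedes the dose. The protocol has no partial-date rule; its statement in Section 10.6 that missing data are not imputed concerns immunogenicity.

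**The concern.** A mid-month or mid-year default is harmless for a descriptive date. It is not neutral for a date that decides whether an event counts as following a dose. Suppose a dose is given on the 16th or later and an event starts later that month. If the day is missing, the event is dated the 15th, before the dose. It then passes to the previous dose. After Dose 1 there is no previous dose, so it appears to precede treatment. In the other direction, an event late in the window can be dated past its end, and an event before the dose can be dated after it.

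At stake are the windowed tables of unsolicited AEs and SAEs, which serve the secondary safety objective. No success criterion depends on them.

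**Working it through.** The plan states no figure to reproduce except its check value: same-day onset gives 0 + 1 = day 1, as the SAP says.

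**Worked example.** Dose 1 is on 5 February, Dose 2 on 22 March (45 days later) and the true onset is on 25 March, with the day missing.
- True onset day after Dose 2: 25 − 22 + 1 = 4.
- Imputed onset is 15 March; relative to Dose 2 this is 15 − 22 + 1 = −6.
- The most recent dose before 15 March is Dose 1: 38 days + 1 = onset day 39, outside its 30-day window.

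The event is counted after neither dose.

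**Enumeration, day missing.** Inputs: the rules in SAP 11.2.1 and the windows in SAP 6.5.1. Assumption: dose dates are uniform over the 365 days of 2017 and true onsets uniform over the days listed. For each pair, the onset is set to the 15th of its month and r = imputed onset − dose date. The event is dated before the dose if r < 0, past the window if r ≥ window length W, and otherwise kept.

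| True onset | W | Pairs | Before dose | Past end | Lost |
|---|---|---|---|---|---|
| Days 0-29 | 30 | 365 × 30 = 10,950 | 1,523 (13.9%) | 1,260 (11.5%) | 25.4% |
| Days 0-41 | 42 | 365 × 42 = 15,330 | 1,523 (9.9%) | 1,260 (8.2%) | 18.2% |
| Days 7-29 | 30 | 365 × 23 = 8,395 | 480 (5.7%) | 1,260 (15.0%) | 20.7% |
| Days 14-41 | 42 | 365 × 28 = 10,220 | 25 (0.2%) | 1,260 (12.3%) | 12.6% |

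The last two rows are the days without home visits after Visits 2-4; most of their loss is past the window end. Protocol Section 3 plans no home visits after the boosters (Visits 10 and 12) or the Control group's doses at Visits 6-8, so the first row applies there.

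**Day and month missing (30 June).** Only 8.2% of events stay in the 30-day window and 11.5% in the 42-day window.

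**Where an event dated before its dose goes.** With 45 days between doses, 99.5% of such events fall in no 30-day window. With 28 days, the protocol's minimum, all fall in the earlier dose's 30-day window: they are misattributed, not lost.

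**Reverse error.** Of partly dated events truly starting 1-14 days before a dose (365 × 14 = 5,110 pairs), 1,260, or 24.7%, are moved into that dose's 30-day window.

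**Scaling.** If a share p of onsets lacks the day, the loss from the 30-day window is about 0.254 × p. The documents give no p. For an assumed 1% to 5%, that is 0.25% to 1.3% of windowed events.

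**The case against.** The strongest case against is that this hardly matters in practice, and much of that stands.

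- After Visits 2-4, staff record solicited and unsolicited events daily in the first one or two weeks, so early onsets there should carry full dates.
- Solicited symptoms are classified from daily recordings per dose (SAP 11.2.5), not from an onset date.
- SAEs and AEs of specific interest are reported within 24 hours of awareness. Seizures have dedicated eCRF screens, and Template 41 lists each SAE with its dose and onset day, so an odd value would be visible.
- Moving an event between doses leaves cumulative SAE counts unchanged.
- Nothing shows that the eCRF accepts partial onset dates, and Protocol 11.1 provides for correcting omissions.
- The rule is the same in all groups, and the safety comparisons are descriptive.

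A reader might infer something stronger: that the rule removes the reactions closest to vaccination and so understates risk. Taken alone, onsets on Days 0-6 do show 40.8% dated before the dose. The documents do not support that as the headline. After Visits 2-4 those are home-visit days, where partial dates are least likely, and nothing suggests that partial dates cluster in the first week after any dose. Nor does the error run one way, since events from before a dose are also pulled in.

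What remains is that the rule, followed as written, gives wrong dose assignments whenever a partial onset occurs, and nothing else in the documents catches this before the windowed tables are built.

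**Conclusion.** The point holds as a fault in a stated rule. For AE and SAE onsets, SAP 11.2.1 should not ignore the dose date. Where the day is missing, roughly a quarter of events leave the 30-day window and just under a fifth the 42-day window, in both cases by a mix of dating before the dose and dating past the end. Roughly a quarter of events from the two weeks before a dose enter its 30-day window. A missing day and month is far worse, because few events keep their window.

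These shares rest on uniform dose dates and onsets and are conditional on the date being partial. The frequency of partial dates is unknown and probably low, so the effect on the reported tables is probably small. It cannot be read as a demonstrated understatement of risk. The primary and secondary immunogenicity conclusions are not affected. One case is left open: a post-Dose 1 event dated before Day 0, which the documents do not say how to count in the cumulative tables.

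The change is worth making because it is cheap and the affected tables are the core of the safety report.

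**What to change.** Add to SAP 11.2.1 a rule for AE and SAE onset dates only:

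- **Day missing, known month contains a study dose:** set onset to that dose date, not later than the stop date, unless the stop date, a visit or report date, or the diary card shows an earlier start. If the month contains two doses, use the later one on or before the stop or report date.
- **Day missing, no dose in the known month:** use the first day of that month.
- **Only the year known:** use the latest study dose in that year on or before the stop or report date.
- **List every imputed onset**, with the recorded partial date and the assigned dose.

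Leave concomitant-medication and non-safety dates under the existing rule. Protocol 6.7.1 has some medication recorded from 30 days before each dose, so moving those starts to the dose date would misclassify prior use.

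Run through the same enumeration, the day-missing rules keep all true post-dose events in the 30- and 42-day windows.

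Cost: one derivation rule and one listing, with no new data. There are two downsides. Partly dated events that truly began shortly before a dose are more often counted after it. If no other timing information were used, the 24.7% above would rise to 75.3% (3,850 of 5,110), so the stop-date, visit and diary checks need to be applied. Imputed onsets will also cluster on Day 1 and slightly inflate the early-window tables. Both err towards counting events as post-dose, the conservative direction for safety.
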